**Original Release: [Month, Day, Year]****Current Version: 2.0****Revision History**

Version Number	Release Date	Section	Change	Reason for Change
2.0		N/A	N/A	Initial release of protocol

## Protocol Synopsis

A Prospective, Post Market, Feasibility Study to Assess the Practical Utility of the OR BlackBox Platform When Used to Compare Surgical Technique During 3D Versus 2D Laparoscopic Bariatric Surgery - The "Black Box" Study

Study Objective	
This is a hypothesis generating pilot study to compare the impact of 2D versus 3D visualization on surgical performance, as measured by the OR BlackBox® platform, during laparoscopic bariatric surgery.

Study Device	
The Olympus HD 2D Laparoscopic Surgical Video System, which is comprised of the following components:
 

• CV-190 Processor

• CLV-190 Light Source

• 3DV-190 3D Visualization Unit

• LMD-X310ST

• IMH-20 Image Capture System

• UHI-4 Insufflator

• K10021611 Cart

• OL-0015-08 Tall Rollstand

• LTF-S190-10 Endoeye Flex 2D

• MAJ-172 tray for 2D scope

• MAJ-2016 8.5M 3G cable

• MAJ-2015 3M 3G cable

 
The Olympus HD 3D Laparoscopic Surgical Video System, which is comprised of the following components:
 

• CV-190 Processor

• CLV-190 Light Source

• 3DV-190 3D Visualization Unit

• LMD-2451MT/2G4 sonly 24" 3D Monitor

• IMH-20 Image Capture System

• UHI-4 Insufflator

**A Prospective, Post Market, Feasibility Study to Assess the Practical Utility of the OR BlackBox Platform When Used to Compare Surgical Technique During 3D Versus 2D Laparoscopic Bariatric Surgery - The "Black Box" Study**

	
 
• K10021611 Cart
 
• OL-0015-08 Tall Rollstand
 
• LTF-190-10-3D ENDOEYE FLEX 3D Videoscope
 
• 3D Glasses (Regular and Clip-on Styles)
 

Other Device(s)	OR BlackBox® Platform
Indications for Use	
The Olympus HD 2D Laparoscopic Surgical Video System is cleared for use in Canada within the thoracic and abdominal cavities including female reproductive organs.
 
The Olympus HD 3D Laparoscopic Surgical Video System is cleared for use in Canada within the thoracic and abdominal cavities including female reproductive organs.

Study Design	Prospective, post-market, hypothesis generating, pilot study
Planned Number of Subjects	
N=50
 
25 subjects will undergo 2 dimensional (2D) laparoscopic surgery
 
25 subjects will undergo 3 dimensional (3D) laparoscopic surgery

Planned Number of Investigational Sites / Countries	1 site in Canada
Primary Endpoint	
There is no primary endpoint for this study as it is a hypothesis generating pilot study.
 
 
• This pilot study will quantify operative performance and intraoperative errors after the introduction of the 2D and 3D technology using the following tools: 
 
◦ Generic Error Rating Tool (GERT)
 
◦ Objective Structured Assessment of Technical Skill (OSATS)
 
 
 

Secondary Endpoints	
 
1. Clinically significant adverse events related to the device(s) and/or procedure. 
 
a. Clinically significant is defined as any deviation from the
 
 
 

A Prospective, Post Market, Feasibility Study to Assess the Practical Utility of the OR BlackBox Platform When Used to Compare Surgical Technique During 3D Versus 2D Laparoscopic Bariatric Surgery - The "Black Box" Study

	
normal surgical or post operative course that requires special treatment or action.
 
 
2. Operating room (OR) team's perception of human factors and teamwork following each procedure using the Modified Surgical Team Assessment Record (STAR) questionnaire.
 
3. NASA Task Load Index to assess mental workload and frustration
 
4. Visualization and Physical Symptoms Questionnaire
 
5. Surgical Team Demographic Questionnaire
 

Follow-up Schedule	
 
1. Screening/Baseline (Clinic Visit): 
 
a. Eligibility criteria
 
b. Informed consent
 
c. Demographics
 
d. Medical history
 
 
 
2. Procedure (Hospital Visit): 
 
a. Laparoscopic 2D or 3D Roux-en-Y gastric bypass surgery
 
b. Adverse events (Including Clavien Classification of Surgical Complications (CCSC))
 
c. Device Deficiencies
 
d. Completion of STAR Questionnaire by each OR team member
 
e. NASA Task Load Index to assess mental workload and frustration
 
f. Visualization and Physical Symptoms Questionnaire
 
g. Surgical Team Demographic Questionnaire
 
 
 
3. Post-Procedure OSATS and GERT 
 
a. Post-Procedure is not a subject follow-up visit, it is the point at which the video and audio feed of each surgical procedure will be reviewed by an Expert Surgical Analyst (ESA) to complete the OSATS and GERT tools.
 
b. The ESA must review video feed within 30 days following each procedure.
 
 
 

**A Prospective, Post Market, Feasibility Study to Assess the Practical Utility of the OR BlackBox Platform When Used to Compare Surgical Technique During 3D Versus 2D Laparoscopic Bariatric Surgery - The "Black Box" Study**

	
4. 30 Day Post Procedure Follow-up (Telephone Call) / End of Study
 
 
Adverse events (Including CCSC)
 
End of study will be reached after completion of the 30 Day Post Procedure Follow-up Telephone Call, subject withdrawal, or lost to follow-up, whichever occurs first.
 

Study Duration	This study is anticipated to take 9 months to complete following IRB approval. Eight months of enrollment and 1 month of follow-up.
Key Inclusion Criteria	
 
≥ 18 years of age
 
Scheduled to undergo elective, primary roux-en-y gastric bypass surgery
 
BMI of 35 to 54.9
 
Willing and able to provide informed consent
 

Key Exclusion Criteria	
 
Previous open abdominal surgery
 
Previous open or laparoscopic upper GI surgery
 
Contraindicated for laparoscopic bariatric surgery
 
Unable or unwilling to provide informed consent
 

Statistical Methods	
Primary Statistical Hypothesis	N/A – This is a hypothesis generating pilot study. As a result no statistical hypothesis will be tested as part of this study.
Statistical Test Method	Outcomes will be assessed using descriptive statistics and comparative analysis.
Sample Size Parameters	
N/A – This is a hypothesis generating pilot study. As a result a sample size calculation is not required.
 
Fifty roux-en-y gastric bypass surgeries will be performed as part of this study; 25 consecutive surgeries will be performed using a 2D laparoscopic camera and 25 consecutive cases will be performed using a 3D laparoscopic camera.

## 1 Introduction

Data published in 2008 estimated the global number of surgical procedures performed annually as 234 million with a rate of major perioperative complications reported between 3% and 17% in industrialized countries. As a derivative of these figures, it is estimated that approximately 7 to 40 million major complications occur worldwide each year. Studies have shown that between 39.6% and 54.2% of surgical complications occur in the operating room (OR); furthermore, it has been suggested that one third to half of all surgical errors are potentially avoidable. These findings have brought considerable attention to quality improvement in the technically demanding field of laparoscopic surgery wherein the risk of intraoperative error is increased by the sociotechnical complexity of the operative environment. In particular, there has been growing interest in evaluating surgical processes from a human factors point of view, as human factors, such as fatigue and mental workload, have become increasingly recognized as root causes of adverse surgical events and outcomes.

Among the most commonly reported errors in conventional laparoscopic surgery are technical errors associated with impaired depth perception; laparoscopic surgeons rely on two-dimensional (2D) video displays to guide their work in a three-dimensional (3D) space, resulting in the loss of depth perception and spatial orientation, as well as the experience of increased visual and cognitive load. Technical errors can be defined as manual errors of the surgeon (e.g. damage to adjacent structures) and procedural errors due to a lack of surgeon proficiency or experience. These errors are frequently described, especially when evaluating closed malpractice cases. These factors have been extensively examined but still remain controversial. A major limitation of error analyses of closed malpractice cases and root cause analyses of complications is the hindsight bias introduced through the knowledge of patient outcome.

Laparoscopic cameras with 3D display functionality were first developed in the early 1990s. The poor image quality produced by early cameras resulted in pronounced physical side effects, including dizziness, headache, and nausea; however, a significant technological advancement in the field of 3D laparoscopy has dramatically improved the usability of these systems. Despite these improvements and the potential for improved surgical safety, the use of 3D laparoscopic equipment remains limited in modern surgical centers. Outdated and conflicting research findings regarding the effectiveness of these systems and the physical side effects associated with their use may be contributing to slow adoption into clinical practice. Furthermore, investigations assessing the impact of 3D laparoscopy on surgical performance in the clinical setting are notably lacking. Thus, robust comparative evaluations of modern 2D and 3D laparoscopic surgical display systems in clinical settings are required to clearly elucidate the impact of 3D laparoscopy on surgical performance and safety with an aim to establish best practices in laparoscopic surgery.

The restoration of stereoscopic vision in laparoscopic surgery has the potential to mitigate these challenges and, to this end, the introduction of 3D stereoscopic displays in laparoscopic surgery may be beneficial to improving surgical safety. The purpose of this study is to compare the impact of 2D versus 3D visualization on surgical performance, as measured by the OR BlackBox® Platform, during laparoscopic Roux-en-Y gastric bypass surgery.

## 2 Device Descriptions

### 2.1 Olympus HD 2D Laparoscopic Surgical Video System

The Olympus HD 2D Laparoscopic Surgical Video System is cleared for use in Canada within the thoracic and abdominal cavities including female reproductive organs and is comprised of the following components:

- CV-190 Processor
- CLV-190 Light Source
- 3DV-190 3D Visualization Unit
- LMD-X310ST
- IMH-20 Image Capture System
- UHI-4 Insufflator
- K10021611 Cart
- OL-0015-08 Tall Rollstand
- LTF-S190-10 Endoeye Flex 2D
- MAJ-172 tray for 2D scope
- MAJ-2016 8.5M 3G cable
- MAJ-2015 3M 3G Cable

### 2.2 Olympus HD 3D Laparoscopic Surgical Video System

The Olympus HD 3D Laparoscopic Surgical Video System is cleared for use in Canada within the thoracic and abdominal cavities including female reproductive organs and is comprised of the following components:

- CV-190 Processor
- CLV-190 Light Source
- 3DV-190 3D Visualization Unit
- LMD-2451MT/2G4 sonly 24" 3D Monitor
- IMH-20 Image Capture System
- UHI-4 Insufflator
- K10021611 Cart
- OL-0015-08 Tall Rollstand
- LTF-190-10-3D ENDOEYE FLEX 3D Videoscope
- 3D Glasses (Regular and Clip-on Styles)

The Olympus HD 2D and 3D Imaging System is lightweight and ergonomically designed with the intention to lessen surgeon fatigue and maximize ease of use. The ENDOEYE FLEX 3D Videoscope allows for 100° of articulation in all directions while maintaining a level visual horizon regardless of viewing angle. Additionally, the system allows for focus free visualization with the ability to toggle back and forth between 2D and 3D imaging.

### **2.3 OR BlackBox® Platform**

The OR BlackBox® “Black Box” Platform is a multi-channel data recorder that records multiple synchronized feeds during a surgical procedure including:

- Panoramic views of the operating room
- View of the laparoscopic camera
- Intraoperative audio
- Room temperature

Video feeds of the room are sent to the Black Box from surveillance cameras that are affixed to the walls inside the OR, and audio feeds are captured using microphones placed at critical locations throughout the room. The Black Box subsequently integrates these recordings into a single interface to provide a comprehensive overview of the operation. The various video perspectives are displayed side-by-side with synchronized audio and a juxtaposed timeline that allows observers to flag any observable errors. This interface allows researchers to study the state of the entire OR for the period of time leading up to, during, and after a flagged error, which is critical for performing root-cause analyses of technical errors.

## **3 Study Objectives**

This is a hypothesis generating pilot study to compare the impact of 2D versus 3D visualization on surgical performance, as measured by the OR BlackBox® platform, during laparoscopic bariatric surgery.

## **4 Study Endpoints**

### **4.1 Primary Endpoint**

There is no primary endpoint for this study as it is a hypothesis generating pilot study. This pilot study will quantify operative performance and intraoperative errors after the introduction of the 2D and 3D technology using the following tools:

- Generic Error Rating Tool (GERT)
- Objective Structured Assessment of Technical Skill (OSATS)

### **4.2 Secondary Endpoints**

1. Clinically significant adverse events related to the device(s) and/or procedure.
  - o Clinically significant is defined as any deviation from the normal surgical or post operative course that requires special treatment or action.

2. Operating room (OR) team's perception of human factors and teamwork following each procedure using the Modified Surgical Team Assessment Record (STAR) questionnaire.
3. NASA Task Load Index to assess mental workload and frustration
4. Visualization and Physical Symptoms Questionnaire
5. Surgical Team Demographic Questionnaire

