## **19 Investigator Responsibilities**

The Principal Investigator of an investigational site is responsible for ensuring that the study is conducted in accordance with the Clinical Trial Agreement, the clinical investigation plan, ISO 14155, ethical principles that have their origins in the Declaration of Helsinki, any conditions of approval imposed by the reviewing IRB/EC, and prevailing local and/or country laws and/or regulations, whichever affords the greater protection to the subject.

The Principal Investigator's responsibilities include, but are not limited to, the following.

- Prior to beginning the study, sign the Clinical Trial Agreement and comply with the Investigator responsibilities as described in such Agreement.
- Prior to beginning the study, sign the Protocol Signature page documenting his/her agreement to conduct the study in accordance with the protocol.
- Provide his/her qualifications and experience to assume responsibility for the proper conduct of the study and that of key members of the site team through up-to-date curriculum vitae or other relevant documentation and disclose potential conflicts of interest, including financial, that may interfere with the conduct of the clinical study or interpretation of results.
- Make no changes in or deviate from this protocol, except to protect the life and physical well-being of a subject in an emergency; document and explain any deviation from the approved protocol that occurred during the course of the clinical investigation.
- Create and maintain source documents throughout the clinical study and ensure their availability with direct access during monitoring visits or audits; ensure that all clinical-investigation-related records are retained per requirements.
- Ensure the accuracy, completeness, legibility, and timeliness of the data reported to the Sponsor in the CRFs and in all required reports.
- Record, report (to Sponsor, and IRB as applicable), and assess every adverse event as applicable per the protocol and observed device deficiency.
- Report to the REC and regulatory authorities any SAEs and device deficiencies that could have led to a SADE and potential/USADE or UADE, if required by the national regulations or this protocol or by the IRB/EC, and supply Olympus with any additional requested information related to the safety reporting of a particular event.

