## **26 Safety Reporting**

### **26.1 Reportable Events by Investigational Site to Olympus**

It is the responsibility of the Investigator to assess and report to Olympus any event which occurs in any of following categories:

- Clinically significant adverse events related to the device(s) and/or procedure.
  - Clinically significant is defined as any deviation from the normal surgical or post operative course that requires special treatment or action
- Device Deficiencies
- Unanticipated Adverse Device Effects/Unanticipated Serious Adverse Device Effects
- New findings/updates in relation to already reported adverse events

When possible, the medical diagnosis should be reported as the Event Term instead of individual symptoms.

If it is unclear whether or not an event fits one of the above categories, or if the event cannot be isolated from the device or procedure, it should be submitted as an AE and/or device deficiency.

Any AE experienced by a study subject during the study procedure through completion of the study must be recorded in the CRF.

Underlying diseases are not reported as AEs unless there is an increase in severity of frequency during the course of the investigation

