### 26.3 Clavien Classification of Surgical Complications

All AEs that occur intra-operatively or within the 30 Day Follow-up period will be assessed using the CCSC:

**Grade I:** Any deviation from the normal post-operative course without the need for pharmacological treatment or surgical, endoscopic, and radiological interventions.

Allowed therapeutic regimens are: drugs as antiemetics, antipyretics, analgetics, diuretics, electrolytes, and physiotherapy. This grade also includes wound infections opened at bedside.

**Grade II:** Requiring pharmacological treatment with drugs other than such allowed for Grade I complications. Blood transfusions and total parenteral nutrition are also included.

**Grade III:** Requiring surgical, endoscopic or radiological intervention.

**Grade IIIa:** Intervention not under general anesthesia

**Grade IIIb:** Intervention under general anesthesia

**Grade IV:** Life-threatening complication (including CNS complications) requiring IC/ICU management.

**Grade IVa:** Single organ dysfunction (including dialysis)

**Grade IVb:** Multi-organ dysfunction

**Grade V:** Death of a patient

**Suffix “d”:** If the patient suffers from a complication at the time of discharge the suffix “d” (for disability) is added to the respective grade of complication. This label indicates the need for a follow-up to fully evaluate the complication.

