### 26.4 Relationship to Study Device

The Investigator must assess the relationship of an AE to the study device and procedure. Relationship classification criteria is defined in Table 3.

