## **29 Conflict of interest**

### **Dual roles**

There is a conflict of interest due to the dual roles of [name] as study subject and P.I. as well as with respect to his involvement in the development of recording and analytic technology. However, [name] will not participate in the evaluation of any recorded procedures. Our analysts will be using objective, closely defined rating, and inter-rater

agreement with a second, blinded rater will continuously be monitored to ensure objectivity of evaluation. The data will be de-identified for the duration of the follow-up period during which the outcome measures will be assessed (30 days), after this period the link code to the data set will be destroyed and the data will be anonymous. The PI will have access to the data content of the de-identified and anonymized dataset. The linking code, however, will not be made available to minimize the risk of bias being introduced by the PI. The PI will know the clinical outcome of each patient but will not have access to the technical and non-technical data until the treatment phase has been completed at 30 days.

The technology used in the study is provided by Surgical Safety Technologies (SST, Toronto, Canada), a company owned by [name] and in which St. Michaels' Hospital has shares. The company is physically located at St. Michael's Hospital.

The aggregate non-identifiable, data will be analyzed using technology provided by the SST and in that form the data will be shared with the company.

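### The between-arm safety endpoint depends on an arm-aware causality judgement that an all-cause, Clavien-graded summary of data already collected would avoid

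*Combined protocol and SAP*

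**What the plan says.** The first secondary endpoint, worded alike in the synopsis, Section 4.2 and Section 11.1.2, is "Clinically significant adverse events related to the device(s) and/or procedure". Clinical significance means "any deviation from the normal surgical or post operative course that requires special treatment or action". No all-cause AE endpoint and no Clavien-grade endpoint is listed.

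On who decides, Section 26.4 states: "The Investigator must assess the relationship of an AE to the study device and procedure". Section 26.1, whose reportable categories include the endpoint's own wording, states: "It is the responsibility of the Investigator to assess and report to Olympus any event which occurs in any of following categories". Section 19 lists among the PI's duties to "assess every adverse event as applicable per the protocol and observed device deficiency". Under Section 9.2 the PI performs the gastrojejunostomy in the study procedures and a fellow performs the jejunojejunostomy.

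On what is collected, Section 26.1 states: "Any AE experienced by a study subject during the study procedure through completion of the study must be recorded in the CRF". Section 26.3 adds: "All AEs that occur intra-operatively or within the 30 Day Follow-up period will be assessed using the CCSC". Section 9.4 collects AEs with the Clavien grade at the 30-day call.

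On analysis, the synopsis foresees descriptive statistics and comparative analysis, and Section 11.4 names the t-test and Chi-square test. Section 11.2 says that no hypothesis will be tested.

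**The concern.** An event enters the 2D/3D safety comparison only after two judgements: that it is related, and that it called for treatment or action. Both fall to an Investigator who, if this is the operating PI, knows which system was used. If the threshold for calling an event related differs between arms, even unintentionally, the counts differ without any true difference in safety. In arms of 25, a few such decisions would show in the result.

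The plan protects its performance ratings against this kind of bias. The expert analysts are kept out of the OR (Section 9.3), the PI does not evaluate recordings, and a second, blinded rater is used (Section 29). None of these measures reaches AE attribution. Section 5.3 says that the data may generate a hypothesis for a larger pivotal study, so a safety signal free of the causality filter would be useful.

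**Working it through.** The plan gives no alpha, power, design event rate or sample-size calculation, so there is no figure to reproduce. The check is mainly a comparison of sections, with simple arithmetic for scale.

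**1. Who makes the judgement.** Sections 26.1 and 26.4 say the Investigator. Section 19 makes AE assessment a PI duty, there is one site, and Section 9.2 has the PI operating. That the assessor operated and knew the system is therefore a strong inference, not an explicit statement. Section 20 contemplates delegation of tasks, and Section 6.4 mentions a further participating staff surgeon. No section names an independent or masked AE assessor.

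**2. How tight the filter is.**
- Relatedness may be to device or procedure, and the procedure is the bypass operation itself.
- Section 26.1 has unclear events submitted.
- Table 3 classifies events that cannot be assessed as possible.
- However, Table 3 has five categories, from not related to definite, and no section says which of them count as related for the endpoint.
- Need for treatment or action is not mapped to Clavien grades. Grade I in Section 26.3 allows several drug classes and bedside wound opening, so that boundary is also open.

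The filter is broad, but its edge is undefined.

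**3. Weight of one decision.** With 25 subjects per arm, 1/25 = 4 percentage points for each subject whose only event is judged in or out.

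**4. Scale of counts (illustrative).** The only complication rate in the documents is 3% to 17% (Section 1), for major perioperative complications across all surgery. It is background, not a design assumption for this trial. It gives 25 × 0.03 = 0.75 to 25 × 0.17 = 4.25 subjects per arm.

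**5. Effect of differential attribution (illustrative).** Let p be the true event rate, equal in both arms, and q_A and q_B the proportions of events judged to qualify in each arm. The spurious difference is p × (q_A − q_B).
- For each 10-point gap in attribution: 0.03 × 0.10 = 0.3 points and 0.17 × 0.10 = 1.7 points.
- With q_A = 90% and q_B = 70%: 0.03 × 0.20 = 0.6 points and 0.17 × 0.20 = 3.4 points.
- With q_A = 90% and q_B = 50%: 0.03 × 0.40 = 1.2 points and 0.17 × 0.40 = 6.8 points, or 25 × 0.068 = 1.7 subjects per arm.

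The attribution proportions are assumptions with no source in the documents. Which arm is A is arbitrary.

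**6. Whether the unfiltered data exist.** Sections 26.1 and 26.3 together give a recorded and Clavien-graded AE set regardless of relatedness, over the period needed. No visit, form or subject has to be added.

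**The case against.** The strongest reply is that the relatedness filter is nearly empty. With the operation itself counted as a cause, unclear events submitted and unassessable ones classed as possible, few complications would drop out. Whether treatment was given is largely a chart fact, open to source verification and monitoring (Sections 12.1 and 24). The endpoint matches the sponsor's reporting category, is one of five secondary endpoints in a pilot without a hypothesis test, and an all-AE table could be produced at reporting in any case. Most of this stands, and it limits the likely bias. It does not show that the filter helps the comparison: where nearly every event passes, the filter adds little, and where some do not, it can distort.

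Three stronger readings are tempting, and the documents do not support them.
- A reader might infer that the declared conflict tilts the safety comparison. Section 29 does say "There is a conflict of interest due to the dual roles of" the PI as investigator and study subject, and it also cites involvement in developing the recording and analytic technology. That technology is used in all study procedures, and both visualization systems are the sponsor's. No interest in either arm is documented.
- A reader might infer from the 3% to 17% range that one or two judgements would create or remove the whole difference. That range covers major complications, which are the events least likely to be judged unrelated or to need no action. The 4-point step also applies to any binary endpoint with 25 per arm, including the one proposed here.
- A reader might infer that an all-cause count would make the comparison unbiased. The same unmasked site staff would still decide what to record and, as far as Section 26.3 shows, how to grade it.

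**Conclusion.** The point holds in moderate form. The plan's only patient-safety endpoint passes through a causality and significance judgement made, on the natural reading, by an operator who knows the arm, with no masked or independent assessor. The data for a summary without that judgement are already required.

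The possible bias is probably modest and has no known direction. The only size that follows from the design is 4 percentage points per reclassified subject. The 0.6 to 6.8 point illustrations for attribution gaps of 20 to 40 points rest on assumed proportions and a background rate for a different class of events. The conclusion assumes that the PI, or someone equally aware of the system used, makes the assessments, and that arms will be compared on safety at least descriptively, as the synopsis suggests. It does not invalidate the pilot or its performance measures, but it should be changed because the remedy is cheap.

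**What to change.** In the synopsis, Section 4.2 and Section 11.1.2, make the between-arm safety summary the number of subjects per arm with at least one AE from the procedure to the 30-day call, regardless of relatedness. Tabulate it by each subject's highest Clavien grade, so that minor Grade I events stand apart from higher grades. Keep the current related and clinically significant events as a supportive summary, and state which Table 3 categories count as related there.

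The cost is a change of wording and one extra table, with no new data. Unrelated or minor events will add some noise, which the split by grade helps contain. AE recording and Clavien grading remain unblinded, so the change removes the causality filter but not all assessor bias. The report should say so.
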